#### **Duration of treatment:**

APR-246 and azacitidine maintenance therapy will continue for a maximum of 12 cycles or until one of the following criteria applies:

- Evidence of disease relapse defined as  $\geq 5\%$  blasts for AML patients or  $>5\%$  blasts for MDS patients. Patients who are continuing to derive clinical benefit in the opinion of the investigator may remain on study treatment following relapse.
- Inter-current illness that prevents further administration of treatment.
- Unacceptable adverse event (AE)(s).
- Patient decides to withdraw from treatment.
- General or specific changes in the patient's condition render the patient unacceptable for further treatment in the judgment of the investigator.
- Patient begins other treatment for underlying disease (i.e., MDS or AML).
- Grade 3-4 acute GVHD or Severe chronic GVHD.

If the patient discontinues treatment early, then the reason for treatment discontinuation and the date the patient was removed will be documented. Patients removed from treatment for unacceptable AEs will be followed until resolution or stabilization of the AE.

Patients may continue to receive study treatment in the setting of relapse or progression, up to a maximum of 12 cycles, provided they are continuing to derive benefit in the opinion of the Investigator.

**Criteria for evaluation:**

Efficacy: Bone marrow aspirate and biopsy following cycle 3, cycle 6, cycle 9, and cycle 12, or when clinically indicated, and monthly CBC.

Safety: CTCAE v5.0. Weekly history and physical for AE assessment (CTCAE v5.0), including CBC with diff, CMP and LDH for the first month on treatment, then monthly.

GVHD assessment (Harris, 2016; Jagasia, 2015) will be performed weekly for the first month on treatment, then monthly.

PK: Cycle 1 only. Pre-dose, 45 min (+/- 5min) after SOI, at EOI (4 hr +/- 30 min after SOI), 5-6 hr after SOI, 24 hr after SOI/Day 2 (before Day 2 dose).

**Statistical Methods:**

Demographic and clinical variables for the study patients will be summarized using descriptive statistics (mean, standard deviation, median, inter-quartile range, range, frequency counts and percentages). Safety and efficacy data will be analyzed overall as well as separately for each dose cohort when appropriate.

**Analysis Populations:**

**Safety Evaluable Population:**

All subjects who are registered on the study and received any dose of APR-246 or azacitidine.

**Efficacy Evaluable Population:**

All subjects who are registered on the study and received at least one dose of APR-246 or azacitidine, and have at least one efficacy assessment, or had

relapse/progression.

### **Sample Size:**

The primary endpoint of the study is the relapse-free survival (RFS) at 12 months. The primary analysis will be done using Kaplan-Meier methodology. Based upon the published data, the risk of relapse and non-relapse mortality in *TP53* mutated MDS is assumed to be ~40% and ~30% at 1 year, respectively. Thus, the assumptions used for the sample size determination are:

- the null hypothesis: the RFS at 1 year is 30%,
- the alternative hypothesis: the RFS at 1 year is 50% or higher,
- accrual time: 24 months,
- follow-up time: 12 months,
- the RFS follows the exponential distribution.

With a one-sided significance level of 10%, 31 subjects will provide 90.1% power to test the null hypothesis against the alternative. The expected number of events during the study is 23 and the power was computed by a one-sided one-sample logrank test. The final analysis will be conducted when the follow-up time for all censored patients exceed 12 months. The null hypothesis will be rejected if a one-sided p-value by the log-rank test is less than or equal to 0.1.

### **Efficacy Analyses:**

All efficacy analyses will be provided by using Efficacy Evaluable population.

### **Relapse-Free Survival**

The primary endpoint, RFS, is defined as the time from the date of registration to disease relapse after SCT, or death, whichever occurs earlier. If patients discontinued treatment due to toxicity, and withdrew consent without relapse disease (RD) or death at the time of data cut off, RFS will be censored at the date of the last assessment.

RFS will be analyzed using Kaplan-Meier methodology. Kaplan-Meier curves will be plotted. Median relapse-free survival will be estimated and their 95% confidence intervals based on Brookmeyer-Crowley methodology will be calculated.

### **Event-Free Survival (EFS)**

EFS is defined as from registration to the first of: morphologic disease relapse, death from any cause, reappearance of a pre-transplant cytogenetic alteration, donor lymphocyte infusion (DLI) for the purpose of treating MDS/AML, or

institution of anti-MDS/AML therapy.

### **Overall Survival**

Overall survival (OS) is defined as the number of days from the date of registration to the date of death, irrespective of the cause. In the event of no death, overall survival will be censored at the last known alive date.

OS will be analyzed using the similar methods as RFS.

### **Non-Relapse Mortality (NRM)**

NRM is defined as time to deaths without relapse/recurrence. Deaths from any cause without prior progression are events. Events related to the disease such as relapse and progression are competing events. Patients lost to follow-up are censored.

NRM will be analyzed using the similar methods as RFS.

### **Time to Progression (TTP)**

Time to progression or relapse is time to first event related to the disease, such as disease progression, disease relapse/recurrence, death from disease progression, and/or initiation of any therapy given to prevent relapse. Deaths without prior relapse/recurrence (i.e., NRM) are competing events.

TTP will be analyzed using the similar methods as RFS.

### **Safety Analyses:**

Safety data including adverse events, vital signs, laboratory data, ECG, physical exam will be tabulated for the Safety Evaluable population. Adverse events will be tabulated by body system, preferred term, severity, and relationship. The tabulation of laboratory parameters will include the normal ranges for each parameter. Each value will be classified as falling above, below, or within the normal range. Laboratory parameters will also be tabulated by maximum NCI-CTCAE v5 severity grade. Incidence and grade of acute and chronic GVHD at 1-year and cumulative will be summarized by number (%) of subjects for each dose level and overall.

## **LIST OF ABBREVIATIONS**

AE	adverse events
----	----------------

ALT	alanine aminotransferase
AML	acute myeloid leukemia
AST	aspartate aminotransferase
AUC 0-inf	area under curve, time 0 to infinity
BM	bone marrow
CFR	Code of Federal Regulations
C max	maximum concentration
CBC	complete blood count
CIBMTR	Center for International Blood and Marrow Transplant Research Repository
CMP	complete metabolic panel
CNS	central nervous system
CPAP	continuous positive airways pressure
CR	complete remission
CRi	complete remission with incomplete blood recovery
CRp	complete remission with incomplete platelet recovery
CRF	case report form
CTCAE	Common Terminology Criteria for Adverse Events
DLI	donor lymphocyte infusions
DNA	deoxyribonucleic acid
ECG	electrocardiogram
EFS	event-free survival
ECOG	Eastern Cooperative Oncology Group (performance status)
EOI	end of infusion
EOT	end of treatment
ESA	erythropoiesis-stimulating agents
GCP	Good Clinical Practice
GFR	glomerular filtration rate
GVHD	graft versus host disease
HCT	hematopoietic cell transplant
HIPAA	Health Insurance Portability and Accountability Act Authorization
HSCT	hematopoietic stem cell transplant
IB	Investigator's Brochure
ICH	International Council for Harmonisation
IHC	immunohistochemistry
IMP	investigational medicinal product
iv	intravenous
IPSS	International Prognosis Scoring System
IRB/IEC	Institutional Review Board/Independent Ethics Committee
LDH	lactate dehydrogenase
LLN	lower limit normal
LTFU	long term follow-up
LVEF	left ventricular ejection fraction
MAC	myeloablative conditioning
MDS	myelodysplastic syndromes
MRD	minimal residual disease

ms	millisecond
NCCN	National Comprehensive Cancer Network
NCI	National Cancer Institute
NGS	next generation sequencing
NMA	non-myeloablative conditioning
NMT	no more than
NRM	non-relapse mortality
OS	overall survival
PB	peripheral blood
PK	pharmacokinetics
PLD	pegylated liposomal doxorubicin
PRBC	packed red blood cells
QTc and QTcF	corrected QT interval, by Fredericia
RBC	red blood cells
RD	relapse disease
RFS	relapse-free survival
RIC	reduced intensity conditioning
RP2D	recommended phase II dose
sc	subcutaneous
SOI	start of infusion
T 1/2	half-life
TBL	total bilirubin
TTP	time to progression
ULN	upper limit normal
URD	unrelated donor
VAF	variant allele frequency
WHO	World Health Organization

## 1.0 GENERAL INFORMATION

### 1.1 Protocol Number and Title of the Study

A19-11172: Phase II trial of APR-246 in combination with azacitidine as maintenance therapy for *TP53* mutated AML or MDS following allogeneic stem cell transplant

## 2.0 BACKGROUND INFORMATION

### 2.1 Introduction

Transplantation of healthy hematopoietic stem cells from an allogeneic donor (HSCT) is the only curable treatment option to improve outcomes for otherwise incurable myeloid diseases such as acute myeloid leukemias (AML) and myelodysplastic syndromes (MDS). With the development of safer transplant conditioning regimens and supportive care measures, transplant can now be offered as a potential curative option to a wider population. However, the potential benefits can be offset by potential resurgence of the disease after HSCT. Disease recurrence is a major cause of treatment failure in patients with AML or MDS who undergo allogeneic HSCT to treat high risk disease, with limited treatment options in the post-HSCT relapsed setting. Thus maintenance strategies need to be explored after transplantation to prevent disease recurrence and improve upon survival.

### 2.2 *TP53* Mutations in MDS and AML

Next generation sequencing (NGS) is becoming more commonly employed as a means to provide detailed and rapid assessment of genome studies that continues to enhance the diagnostic, prognostic, and therapeutic capabilities within myeloid malignancies. Most commonly utilized NGS myeloid panels incorporate 20-50 genes and can identify mutations in the vast majority of patients, several of which have been independently associated with decreased survival. More recent investigations have uncovered the most negative prognostic factor in MDS patients noting the impact of the mutation status of *TP53*. Not only are (non-benign) *TP53* mutations associated with decreased OS in mutated patients, but also predicts poor response and resistance in patients treated with the only currently available FDA-approved disease modifying agents in MDS, lenalidomide and azacitidine (AZA). Similarly, patients with AML with evidence of *TP53* mutation are associated with NCCN poor risk AML, complex karyotype, and monosomal karyotype and demonstrate poor overall survival and relapse-free survival similar to what has been reported in MDS.

### 2.3 *TP53* Mutations in HCT

Genetic profiling of patients at time of undergoing HSCT continues to inform clinicians regarding risk stratification of allogeneic transplant recipients. Mutations of *TP53* strongly predict for lack of benefit to HCT, and additionally demonstrate the prognostic significance of *TP53* mutation as patients with complex karyotype without

mutant *TP53* had similar survival to patients with normal karyotype. Using the Center for International Blood and Marrow Transplant Research Repository (CIBMTR), Lindsley and colleagues furthermore reported the largest data analysis to date on the prognostic impact genomic mutations in HSCT recipients for MDS. At least 1 genomic abnormality was detected in nearly 80% of patients who underwent HSCT. *TP53* mutations were represented in 19% of all patients and at a higher frequency (34%) in patients with Intermediate-2 or High Risk stratification by the International Prognosis Scoring System (IPSS). In multivariate analysis, *TP53* was independently associated with shorter survival and shorter time to relapse in comparison to no evidence of *TP53* mutation. Three-year overall survival for *TP53* mutated patients was 20% with median overall survival of approximately 8 months, in comparison to those that did not have *TP53* mutation having a median OS of approximately 2 years. This study underscores the importance of alternative strategies for *TP53* mutated patients particularly those eligible curable intent therapy utilizing HSCT.

## 2.4 Azacitidine After Allogeneic HCT

Azacitidine (AZA) is a DNA methyltransferase inhibitor that shows significant clinical activity in both MDS and AML. Additionally, AZA has been shown to an effective salvage therapy in patients who relapse after HCT. Given the efficacy of AZA in these settings, maintenance strategies have been evaluated post-allogeneic transplant to prevent disease recurrence. The efficacy of low-dose AZA after allogeneic transplantation was originally reported in AML and subsequently in a larger phase I dose finding study including AML and MDS patients. In a cohort of forty-five patients who receive 4 cycles of post-HCT AZA, one year event-free survival and overall survival were reported as 58% and 77%, respectively, with reversible thrombocytopenia noted to be the dose-limiting toxicity. Tolerability and efficacy of AZA for one year after HCT has been reported by Craddox et al. Thirty seven patients were treated in AZA in the peri-transplant period with the day 100 and 1 year NRM was 0% and 8%, respectively, with no patients having any evidence of chronic graft versus host disease, underscoring the tolerability of the treatment. The 1-year and 2-year RFS were 57% and 49%, respectively, with patients demonstrating CD8+ T cell response demonstrating reduced relapse rate. Thus AZA dosing of 36 mg/m^2 subcutaneously for five consecutive days is effective and tolerable, and will be utilized at this dose for this study.

## 2.5 APR-246

A series of 15 horizontal black bars of varying lengths, decreasing in length from left to right. The bars are set against a white background.

## 2.6 Rationale for Current Study

A series of horizontal black bars of varying lengths, arranged vertically. The bars are solid black with no texture or shading. The lengths of the bars decrease from top to bottom. The bottom-most bar is the longest and contains a single small white square in its center.

A series of horizontal black bars of varying lengths, with a small black square at the bottom left.

## 2.7 Number of Patients

Approximately 31 patients.

## 2.8 Potential Risks

A series of horizontal black bars of varying lengths, likely representing redacted text or data. The bars are arranged vertically and span the width of the page.

A horizontal bar composed of five thick black lines. The lines are evenly spaced and extend across the width of the frame. In the bottom right corner, there is a small, solid black square.

A series of horizontal black bars of varying lengths, arranged vertically. The second bar from the left contains a small white 'C'.

A series of six horizontal black bars of varying lengths, decreasing from left to right. The first bar is the longest, followed by a shorter one, then a very long one, then another very long one, then a short one, and finally the shortest bar on the far right.

11. **What is the primary purpose of the *Journal of Clinical Oncology*?**

## 2.9 Characteristics of a Well-Conducted Trial

The following characteristics of an adequate and well-conducted trial will be implemented:

1. The Investigators will be well qualified by scientific training and experience.
2. Detailed Case Report Forms (CRFs) will be completed for every patient.

3. Requirements for institutional ethics review as set forth by the appropriate Institutional Review Board/Independent Ethics Committee (IRB/IEC), Title 21 Code of Federal Regulations (CFR) Part 56, the European Union Directive 2001/20/EC and its associated Detailed Guidances, European Union GCP Directive 2005/28/EC, the ICH Guideline for Good Clinical Practice, Sections 3 and 4, and the terms of the Declaration of Helsinki (2013), will be followed.
4. Requirements for informed consent in accordance with institutional guidelines, FDA requirements as specified in Title 21 CFR, Part 50, the European Union Directive 2001/20/EC and its associated Detailed Guidances, European Union GCP Directive 2005/28/EC, the ICH Guideline for Good Clinical Practice, Section 4.8, and the terms of the Declaration of Helsinki (2013), will be followed.
5. Safety data will be recorded and evaluated.
6. Routine monitoring visits will be conducted by the Sponsor's representative ( [REDACTED] ) to ensure data accuracy.
7. Drug accountability will be strictly maintained.
8. This trial will be conducted according to Good Clinical Practice (GCP), the protocol and applicable regulatory requirements.

### **3.0 TRIAL OBJECTIVES AND PURPOSE**

#### **3.1 Primary Objectives**

1. To assess relapse-free survival (RFS) in patients with *TP53* mutated AML or MDS who receive combination maintenance treatment with APR-246 with azacitidine after undergoing allogeneic hematopoietic stem cell transplant (HSCT).
2. To evaluate the safety and tolerability of APR-246 in combination with azacitidine as maintenance treatment post-HSCT.

#### **3.2 Secondary Objectives**

1. To assess the overall survival (OS).
2. To assess non-relapse mortality (NRM).
3. To assess time to progression (TTP).
4. To evaluate cumulative incidence of Grades II-IV and III-IV acute graft versus host disease (GVHD).
5. To evaluate 12-month cumulative incidence of mild, moderate, and severe GVHD.
6. To describe event-free survival (EFS).

#### **3.3 Exploratory Objectives**

1. To examine the effect of pre- and post-transplant MRD (*TP53* variant allele frequency, VAF) on RFS and OS.
2. To determine if p53 protein expression and other potential genomic biomarkers at baseline before and after HSCT predicts potential effect on RFS and OS.
3. To determine if *TP53* clonal suppression (serial VAF in bone marrow) after HSCT correlates with outcomes.
4. To evaluate APR-246 plasma pharmacokinetics (PK) when administered with azacitidine after transplantation.
5. To evaluate post-transplant donor engraftment via chimerism studies in blood and bone marrow.

### 3.4 Endpoints

#### 3.4.1 Primary Endpoints

1. RFS
2. Incidence, severity, relatedness of adverse events (AEs) and/or laboratory abnormalities

#### 3.4.2 Secondary Endpoints

1. OS
2. NRM
3. Time to progression or relapse
4. Incidence and grade of acute and chronic GVHD (cumulative)
5. Incidence and grade of acute and chronic GVHD (1-year)
6. EFS

#### 3.4.3 Exploratory Endpoints

1. MRD defined by *TP53* VAF
2. RFS and OS in relation to baseline p53 protein expression (IHC) and other potential genomic biomarkers
3. RFS and OS in relation to clonal suppression, i.e., depth and duration of *TP53* VAF reduction in BM samples repeated every 3 months
4. PK parameters:  $C_{max}$ ,  $AUC_{0-inf}$ ,  $T_{1/2}$
5. Post-transplant donor engraftment via chimerism studies in blood and bone marrow (whole marrow and CD3/CD33 fractions)

## 4.0 TRIAL DESIGN

### 4.1 Overview of Trial Design

This is a multi-center, open label, Phase II clinical trial to assess the safety and efficacy of APR-246 in combination with azacitidine as maintenance therapy after allogeneic HSCT for patients with *TP53* mutant AML or MDS.

To be eligible to participate in this study, all patients must have either: 1) pre-screening NGS on peripheral blood (PB) or bone marrow (BM) samples at time of HSCT work up to determine presence of *TP53* mutation status or, 2) previously documented evidence of *TP53* mutation by NGS on PB or BM samples.

[figure not shown]
Patients will sign consent and be prescreened for *TP53* mutant AML or MDS before they have a HSCT (Day 0). During the post-HSCT period (Day 1 to 100 post-HSCT), patients are screened for eligibility to receive APR-246 and azacitidine maintenance treatment. In order to proceed with APR-246 and azacitidine treatment, neutrophil and platelet engraftment (recovery) must be confirmed between Day 30 to Day 100 post-HSCT. APR-246 and azacitidine must be initiated no more than 28 days after confirmation.

APR-246 will be administered on Days 1-4, with azacitidine on Days 1-5, of every 28 day cycle. Patients may receive a maximum of 12 cycles of treatment. Patients may continue to receive study treatment in the setting of relapse or progression, up to a maximum of 12 cycles, provided they are continuing to derive benefit in the opinion of the Investigator.

[figure not shown]
A safety evaluation will be performed by the Safety Monitoring Committee after the first 6 patients have completed 1 cycle of APR-246 and azacitidine combination therapy. The Committee will decide if it is appropriate to continue at the current dose; or, in the event the combination is not tolerated (e.g. patients experience dose limiting toxicity) the dose of APR-246 will be reduced for subsequent patients.

## Figure 1: Trial Overview

### Enrollment, Pre-screening, Pre-/Post-HSCT APR-246 Screening

### APR-246 and Azacitidine Treatment Period, EOT and LTFU

### 4.2 Safety Evaluation-First 6 Patients

A safety evaluation will be performed by the Safety Monitoring Committee after the first 6 patients have completed 1 cycle of APR-246 and azacitidine combination therapy. If >1 of 6 patients experience any of the following toxicities, then the APR-246 dose will be reduced for subsequently enrolled patients.

- Treatment related non-hematological CTCAE grade 3-4 toxicity that lead to dose modification or withdrawal.
- Absolute neutrophil count (ANC) not recovering to  $>500/\mu\text{L}$  by day 56 of a cycle in the absence of active leukemia/myelodysplasia.
- Grade 3 metabolic/electrolyte abnormalities that are clinically significant, and not adequately controlled within 72 hours.

- Grade 3 nausea/vomiting/diarrhea or CNS toxicity that does not resolve within 28 days despite treatment interruption and maximum medical therapy.

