#### **4.5 Duration of Therapy**

Maintenance therapy will continue for a maximum of 12 cycles (28 days/cycle) from first dose of APR-246, or until one of the following criteria applies:

- Evidence of disease relapse defined as  $\geq 5\%$  blasts for AML patients or  $>5\%$  blasts for MDS patients. Patients who are continuing to derive clinical benefit in the opinion of the investigator may remain on study treatment following relapse.
- Inter-current illness that prevents further administration of treatment.
- Unacceptable AEs.
- Participant decides to withdraw from treatment.
- General or specific changes in the patient's condition render the patient unacceptable for further treatment in the judgment of the investigator.
- Participant begins other treatment for underlying disease (MDS or AML).
- Grade 3-4 acute GVHD or Severe chronic GVHD.

If the participant discontinues treatment early, then the reason for treatment discontinuation and the date the participant was removed will be documented. Participants removed from treatment for unacceptable AEs will be followed until resolution or stabilization of the AE. Participants that discontinue treatment early will continue to be followed for relapse, if not yet documented, and survival.

Patients may continue to receive study treatment in the setting of relapse or progression, up to a maximum of 12 cycles, provided they are continuing to derive benefit in the opinion of the Investigator.

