### **Other toxicity**

All dose modifications, interruptions or discontinuations must be based on the worst preceding toxicity as graded by the NCI Clinical Toxicity Criteria (NCI-CTCAE version 5). Once a dose has been reduced during a treatment cycle, re-escalation will not be permitted during any subsequent cycle (with exception of CNS events). If the administration of APR-246 is interrupted for reasons other than toxicity, then treatment with APR-246 may be resumed at the same dose. The same provision applies if the patient experienced an unacceptable toxicity not specifically described in this section, provided that this toxicity resolved to ≤ CTCAE grade 1, unless otherwise specified.

Day 1 of next cycle treatment with APR-246 and azacitidine can be delayed for up to 4 weeks (28 days) to allow for count recovery at Investigator discretion pending discussion with the Sponsor and Medical Monitor. Non-hematologic grade 4 treatment related adverse events will lead to permanent discontinuation, irrespective of recovery time, unless otherwise specified.

Exceptions would include nausea/vomiting/diarrhea which can be controlled by medications and/or asymptomatic electrolyte imbalances which can be corrected. In addition, in most instances, patients that experience a prolonged treatment interruption because of an adverse event and/or a grade 3 adverse event will decrease the dose of study drug after their recovery (see tables in this section for dose adjustment guidelines).

If any other drug-related grade 3 or 4 toxicity that is not clearly related to azacitidine is observed, APR-246 dose must be reduced for the next and subsequent cycles.

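### The first-six safety count can fall due before two of its four toxicity criteria are readable for the most recently dosed patients, and the protocol does not say how pending cases count

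*Combined protocol and SAP*

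**What the plan says.** Section 4.2 sets the timing: "A safety evaluation will be performed by the Safety Monitoring Committee after the first 6 patients have completed 1 cycle". The Synopsis and Sections 4.1, 8.1.2 and 8.1.4.4 use the same trigger. The decision rule follows: "If >1 of 6 patients experience any of the following toxicities, then the APR-246 dose will be reduced for subsequently enrolled patients".

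Four criteria are listed:

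1. "Treatment related non-hematological CTCAE grade 3-4 toxicity that lead to dose modification or withdrawal". No waiting time is attached.
2. Neutrophils not back above 500/µL "by day 56 of a cycle in the absence of active leukemia/myelodysplasia".
3. Clinically significant Grade 3 metabolic or electrolyte abnormality not controlled within 72 hours.
4. "Grade 3 nausea/vomiting/diarrhea or CNS toxicity that does not resolve within 28 days despite treatment interruption and maximum medical therapy".

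Cycle length is given in Section 4.5: "Maintenance therapy will continue for a maximum of 12 cycles (28 days/cycle) from first dose of APR-246". Section 7.2.4 and Table 10 place the end-of-cycle visit at Day 28. Section 6.2 (Other toxicity) adds that Day 1 of the next cycle "can be delayed for up to 4 weeks (28 days) to allow for count recovery", at the investigator's discretion after discussion with the sponsor and Medical Monitor. Figure 2 shows the same four-week allowance.

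After the first-six evaluation, Section 8.1.4.4 has safety reviewed at routine status meetings, with no threshold. Section 8.1.2 plans no formal analysis.

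**The concern.** The trigger guarantees 28 days of observation for the last of the six patients. Criterion 2 is judged at Day 56. Criterion 4 needs 28 days without resolution, so an event that starts during Cycle 1 cannot qualify until after Day 28. The more-than-one-of-six rule is the only numerical rule that sets the dose for later patients, and it turns on a single patient: one case leaves the dose alone, two lower it. A patient whose status is not yet known can only be left out of the count, so any error runs towards keeping the current dose. The text has no category for a pending case and no numerical re-count once the outstanding patients have been read.

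**Working it through.** **Inputs.** Trigger, rule and criteria: Section 4.2. Cycle of 28 days: Section 4.5. Delay of up to 28 days: Section 6.2. Accrual of 31 patients in 24 months: Section 9.2. The protocol states no operating characteristic for this rule, so there is no figure of its own to reproduce.

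**Step 1: windows against the trigger, nominal 28-day cycle.**
- Criterion 2: Day 56 against 28 days of follow-up for patient six, a shortfall of 56 − 28 = 28 days.
- Criterion 4, read as running from onset (the text gives no starting point): onset on Day k can qualify no earlier than Day k + 28. That is Day 29 for a Day 1 onset and Day 56 for a Day 28 onset.
- Criteria 1 and 3 have no long window.

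**Step 2: how many of the six are short.** Patient six always has under 56 days when reaching Day 28. An earlier patient is short if dosed within the 28 days before patient six. Assume treatment starts follow a Poisson process at the planned average rate:
- Rate = 31/24 = 1.29 per month, or one per 23.6 days.
- Expected other starts in 28 days = 28/23.56 = 1.188.
- Mean number short = 1 + 1.188 ≈ 2.2 of 6 (the cap at six changes this negligibly).
- P(only patient six short) = exp(−1.188) = 0.305, so P(at least two short) = 0.695.
- At twice the accrual rate the mean is 3.3.

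**Step 3: effect on the rule.** Let p be the chance per patient of any listed toxicity, and s the part of p that only criterion 2 or 4 can detect and that is still unread. With m patients short, 6 − m count with probability p and m with probability p − s.

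All six readable, p = 0.30 (assumed): P(more than 1) = 1 − 0.7⁶ − 6 × 0.3 × 0.7⁵ = 1 − 0.1176 − 0.3025 = 0.580.

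Example with m = 2, s = 0.10:
- P(0) = 0.7⁴ × 0.8² = 0.1537.
- P(1) = 4 × 0.3 × 0.7³ × 0.8² + 2 × 0.2 × 0.8 × 0.7⁴ = 0.2634 + 0.0768 = 0.3403.
- P(more than 1) = 1 − 0.1537 − 0.3403 = 0.506.

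Averaging over the distribution of m in Step 2, with the total rate and its split assumed:

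| Total rate p | Slow-reading part s | All six readable | At the trigger |
|---|---|---|---|
| 30% | 5 points | 58% | 54% |
| 30% | 10 points | 58% | 50% |
| 30% | all 30 points | 58% | 32% |
| 20% | 5 points | 34% | 30% |
| 20% | all 20 points | 34% | 17% |

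The rows in which all toxicity is slow-reading are the extreme case. They suppose that nothing is detected under criteria 1 or 3.

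**The case against.** A reader might infer that toxicities under criteria 2 and 4 cannot be counted at all when the decision is made, and that the rule's sensitivity is therefore nearly halved. The documents do not support that, for five reasons.

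- **Staggered entry.** The review waits for patient six. On the figures above, about 6 − 2.2 = 3.8 patients already have 56 days. This stands.
- **The delay rule.** A Day 56 within a cycle makes sense only if a cycle can run past Day 28, and 28 + 28 = 56 matches the permitted delay. On that reading, a patient held for count recovery has not finished Cycle 1 and the review waits; a patient who starts Cycle 2 on time would usually have recovered. This is plausible, but Section 4.2 does not invoke the delay, the delay is discretionary, and the schedule closes the cycle at Day 28. The text leaves it open.
- **Overlap with criterion 1.** Table 5 links unresolved Grade 3 CNS or gastrointestinal toxicity to a dose reduction. If treatment-related, such a case meets criterion 1 without waiting 28 days. This stands, but it is partial: criterion 4 carries no relatedness condition, and criterion 1 excludes haematological toxicity, so it cannot replace criterion 2.
- **The trigger is an earliest date.** If the Committee met two weeks after patient six reached Day 28, the mean number short would be 1 + 1.188/2 ≈ 1.6. For toxicity starting on infusion Days 1 to 4, the 28 days end on Days 29 to 32. A short administrative lag therefore helps, but the protocol does not require one.
- **Safety review continues.** Status-meeting review, individual dose-modification rules and the pause after a non-progression death all remain. None of them re-applies the more-than-one-of-six threshold.

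**Conclusion.** The point holds in limited form. The stated timing of the evaluation does not fit two of the four criteria it applies, and the protocol settles neither what a completed cycle means for a delayed patient nor how a pending case counts. On the nominal reading the sixth patient is always affected, and on average about 2.2 of the six are. The count can then be too low, never too high, when it sets the dose for later patients.

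The loss is probably modest: from 58% to between 50% and 54% at a total rate of 30% with 5 to 10 points slow-reading. A fall to 32% needs every listed toxicity to be slow-reading, which nothing in the documents suggests. These figures rest on assumed toxicity rates and splits, treatment starts at the planned average pace, the 28 days of criterion 4 running from onset, and a review held exactly when patient six reaches Day 28. That the timing and the windows conflict on the nominal reading depends on none of the assumed rates.

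**What to change.** Reconcile the trigger (Synopsis and Sections 4.1, 4.2, 8.1.2 and 8.1.4.4) with the criterion windows in Section 4.2 and the delay rule in Section 6.2:

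- Keep the Cycle 1 review, and label its count provisional.
- Declare the more-than-one-of-six count final only when each of the six has passed the longest window the list uses, or has already met a criterion.
- State whether a completed cycle includes the permitted delay, when the 28 days of criterion 4 start, and how a pending case is recorded at the provisional review.

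The cost is a sentence or two, repeated in those places. The final count comes about four weeks later (56 − 28 = 28 days). This change does not itself require an accrual pause. The toxicity criteria, the onset days they cover and the doses remain with the clinical team.
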